8.5 Exploratory Biomarker Assessments

Blood samples for biomarker analysis were to be collected at Screening Visit 2 and Weeks 4, 12, 24, 36, 52 (EOSa), 64, 76, 88, and 104 (EOSb) or ET. Biomarkers that were assessed included, but were not limited to, bone biomarkers (P1NP and β -CTX) and a cartilage biomarker (COMP).

9 STUDY SUBJECTS AND DEMOGRAPHICS

9.1 Disposition of Subjects and Withdrawals

Subject disposition will be presented in a summary table detailing the number and percentage of subjects who were randomized, treated in Phase B, completed Phases A and B of the study, and discontinued (e.g. subject withdrawal, adverse event, etc.) overall and by treatment group. Additionally, subject disposition for randomized subjects will be presented by treatment group and study site. Additional tables will be prepared to summarize the number of subjects enrolled under each protocol version and included in each Phase B analysis set. The disposition for individual subjects will be listed along with additional information on discontinued subjects.

9.2 Protocol Deviations

A protocol deviation is defined as any noncompliance with the clinical trial protocol requirements. The noncompliance may be either on the part of the subject, the Investigator, or the study site staff.

Deviations are summarized into one of the following categories:

- Investigational Product
- Informed Consent
- Enrollment
- Procedures
- Labs/Specimens
- Study Visits
- Source Documentation

- Diaries, Questionnaires, or Patient Reported Outcomes
- Subject Non-Compliance
- Serious Adverse Events

Deviations are categorized as major or minor by a cross-functional team according to pre-defined criteria established in the Protocol Deviation Classification Guideline.

- A major deviation is defined as a divergence from the protocol that materially (a) reduces the quality or completeness of efficacy data, (b) makes the informed consent inaccurate, or (c) impacts a subject's safety, rights or welfare.
- A minor deviation is defined as a divergence from the protocol that deviates from the procedures and guidelines outlined in the protocol, but is not classified as a major deviation (i.e. the deviation does not materially (a) reduce the quality or completeness of the data, (b) make the informed consent inaccurate, or (c) impact a subject's safety, rights or welfare).

Protocol deviations may result in subject exclusion from the PPASB. Prior to Phase B database lock, all protocol deviations were reviewed by study team members to determine if the deviation could reasonably affect/confound interpretation of efficacy endpoints and should result in the subject being excluded from the PPASB. Subjects with the following types of deviations were excluded from the PPASB:

- Subjects taking pain medications that may significantly impact pain and function assessment

A final list of protocol deviations resulting in subject exclusion from the PPAS and PPASB can be found in [Appendix 2](#).

Major protocol deviations that occurred in Phase B will be summarized by site and category, and all protocol deviations will be listed for each subject. Additionally, the COVID-19 pandemic related protocol deviations that occurred in Phase B will be summarized separately.

For deviations associated with a study visit, only those occurring at Week 64, Week 76, Week 88, or Week 104 (EOSb) will count as Phase B deviations. For deviations not associated with a study visit (e.g. prohibited medications), the dates listed in the CRA comments were evaluated against the date of the subject's Week 52 injection. Any deviations that occurred after the Week 52 injection will be counted as Phase B deviations. Details can be found in [Appendix 3](#).

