10.4.7 PLANNED INTERIM ANALYSES

This safety study was initially designed as a one-year double-blind study. The protocol was amended to add a built-in, one-year single blind extension (Phase B) after the formal, one-year core study (Phase A) completes. The primary analysis will be after last subject completes Week 52 in Phase A and should not be considered an interim analysis.

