10.6 MEASURES TO MINIMIZE BIAS

10.6.1 BLINDING PROCEDURES

Phase A is a double-blind study. Study medication will be provided to the investigational center. The investigational center must identify unblinded personnel who are able to prepare and perform the injection of study medication and/or placebo. Study personnel administering or preparing study medication and reference therapy must minimize any contact with the subject following the injection and may not perform any study assessments throughout the duration of the study. Each site will be required to document a blinding plan that identifies the blinded and unblinded personnel at the investigational center and describes how the study blind will be maintained.

Subjects will be assigned a subject number at their Screening Visit 1. On Day 1, eligible subjects will be randomized via the Medidata Rave database. Upon randomization of a subject, a Dispensation email will be sent from [contact] to the designated unblinded investigational staff member(s). Subjects will be randomized 1:1 (0.07 mg active per 2 mL injection : 2 mL placebo) to each treatment group using a permuted block design. Specific information regarding the use of Medidata Rave RTSM to store and implement the permuted block design will be detailed within the SAP.

Primary analysis of Phase A data will be completed after the last subject completes Week 52 (EOSa). While the Sponsor will be unblinded to study treatment after the Phase A analysis, the Investigator and the subject will remain blinded.

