4.3 Treatment Blinding

Phase A of the study was double-blind. Study medication was provided to the investigational center, and the center identified unblinded personnel who were able to prepare and perform the injection of study medication and/or placebo. Study personnel administering or preparing study medication and reference therapy were to minimize any contact with the subject following the injection and not perform any study assessments throughout the duration of the study. Each site was required to document a blinding plan that identified the blinded and unblinded personnel at the investigational center and described how the study blind will be maintained.

Primary analysis of Phase A data was completed after the last subject completed Week 52 (EOSa). While the Sponsor was unblinded to study treatment after the Phase A analysis (after the last subject completed Week 52 [EOSa]), the Investigators and the subjects remained blinded for Phase B.

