12 EFFICACY ANALYSIS

A statistical description of Pain NRS at baseline will be provided along with absolute changes from baseline at each subsequent timepoint for subjects in the FASB and PPASB. Statistical descriptions of WOMAC Pain, WOMAC Function, Patient Global Assessment, and mJSW at baseline will also be provided along with absolute changes from baseline at each subsequent timepoint for subjects in the FASB only.

Changes in the target knee from baseline in Pain NRS will be characterized using MMRM for subjects in the FASB and PPASB; the models will be evaluated through Week 104 (EOSb). All models will use treatment group, week, treatment×week interaction, and baseline values as covariates. Unadjusted 95% confidence intervals and P values will be reported.

If a subject submitted data related to their non-target knee due to an electronic device error, this data will not be analyzed.

Subject-level listings will be provided.

Since Phase A analysis (defined prior to unblinding) was the primary analysis for this study, there will be no estimands provided for Phase B.

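### PPASB pain-medication exclusions were left to study-team judgement after the sponsor was unblinded, and nothing requires the reviewers to be masked to treatment

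*SAP*

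**What the plan says.** - **Blinding.** SAP 4.3: "While the Sponsor was unblinded to study treatment after the Phase A analysis", Investigators and subjects stayed blinded. Protocol 10.6.1 says the same, and Protocol 10.4.7 describes Phase B as single blind.
- **Review.** SAP 9.2 places the review before Phase B database lock: "all protocol deviations were reviewed by study team members to determine if the deviation could reasonably affect/confound interpretation" of the efficacy endpoints and should lead to exclusion from the PPASB.
- **Criterion.** The only exclusion category listed in SAP 9.2 is "Subjects taking pain medications that may significantly impact pain and function assessment".
- **Other criteria nearby.** SAP 9.2 also states: "Deviations are categorized as major or minor by a cross-functional team according to pre-defined criteria established in the Protocol Deviation Classification Guideline". That guideline governs major or minor status, not PPASB membership.
- **Use.** SAP 12 fits the Pain NRS MMRM in both the FASB and the PPASB, with unadjusted confidence intervals and P values, and does not say which set leads. It gives the reason for having no Phase B estimands as follows: "Since Phase A analysis (defined prior to unblinding) was the primary analysis for this study".

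**The concern.** Removing subjects from an analysis set after randomization is safest when those who decide cannot know the treatment. Here the decision was open to judgement, was made after the sponsor was unblinded, and concerned analgesic use, which is plausibly related to the pain score being modelled. If a reviewer knew the assignments, borderline medication records could be treated differently by arm without any intent to do so. The SAP gives no statement that would let a reader of the PPASB result set this aside.

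What is at stake is the credibility of the PPASB Pain NRS result, and of any comparison that uses it to support or qualify the FASB result.

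**Working it through.** No figure in the plan bears on this point: the one design figure, 81.6% power, concerns the BMD ratio. The check therefore sets the passages side by side and adds an illustration of size.

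**1. Timing.** The Phase A analysis, and with it sponsor unblinding, follows the last subject's Week 52 visit, nominally Day 365 (Protocol 7.3.4). Week 104 is nominally Day 729 (Protocol 7.3.5). If that last subject entered Phase B, the gap is 729 − 365 = 364 days. A review of all Phase B deviations could not be finished until about a year after the trigger for unblinding. It could precede unblinding only if the Phase A analysis had been held back by about as long, which nothing suggests; SAP 5.1 reports it as completed.

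**2. Reviewers.** SAP 9.2 does not say who the study team members were. The sponsor leads and conducts the study (Protocol 15.1) and does its data management (Protocol 14.1), and its Medical Monitor notes prohibited therapy as a deviation (SAP 4.4.2). Sponsor staff are thus plausible reviewers, but this is not stated. No passage masks such staff in Phase B.

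**3. How much is discretionary.** A subject in the FASB can be left out of the PPASB in three ways:

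| Route | Source | Basis |
|---|---|---|
| Already outside the Phase A PPAS | SAP 7.5 | Carried over by rule |
| Did not complete Phase B | SAP 7.5 | Rule |
| Phase B deviation judged to affect efficacy evaluation | SAP 7.5, 9.2 | Judgement; pain medication is the one category named |

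Only the third route is in question.

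**4. Possible size (illustration).** The documents give no Pain NRS SD, and no count of exclusions is available in the text reviewed. Assume an arm of N subjects with SD 1, from which k subjects are removed, each D SD from the arm mean in the same direction, with none removed from the other arm.

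- Shift in that arm's mean = k × D / (N − k)
- Standard error of the difference = √(1/N + 1/(N − k))

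N = 50 is the planned arm size (SAP 6); N = 40 is an assumed Phase B size.

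| N | k | Shift, D = 1 | Shift, D = 2 | SE of difference |
|---|---|---|---|---|
| 50 | 1 | 1/49 = 0.020 | 2/49 = 0.041 | 0.201 |
| 50 | 3 | 3/47 = 0.064 | 6/47 = 0.128 | 0.203 |
| 50 | 5 | 5/45 = 0.111 | 10/45 = 0.222 | 0.205 |
| 40 | 1 | 1/39 = 0.026 | 2/39 = 0.051 | 0.225 |
| 40 | 3 | 3/37 = 0.081 | 6/37 = 0.162 | 0.228 |
| 40 | 5 | 5/35 = 0.143 | 10/35 = 0.286 | 0.231 |

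In standard errors, the shift runs from 0.020/0.201 ≈ 0.1 to 0.286/0.231 ≈ 1.2. These are single-time-point means, not the repeated-measures model. Exclusions spread over both arms, or over both ends of the scale, would move the difference less.

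**The case against.** A reader might infer that the reviewers had the treatment codes in hand, or that the PPASB is biased. The documents support neither. They say that the sponsor was unblinded, not that these reviewers saw assignments, and the deviation guideline named in SAP 9.2 is not among the documents reviewed.

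Discretion is also limited. Only a recorded deviation can trigger this route, the prohibited medications are set out in Protocol 7.6 and Appendix 1, and Investigators, who report their use, stayed blinded. What remains open is which pain-medication deviations were serious enough to count.

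The link between pain and analgesic use is a weakness of any per-protocol set and would exist with fully masked reviewers. It raises the stakes but is not evidence of unmasked decisions.

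Some transparency is already planned: the deviations leading to exclusion are assigned to Appendix 2 and all deviations are listed by subject (SAP 9.2), subjects in each Phase B set are counted (SAP 9.1), and baseline characteristics are shown by arm for the FASB and PPASB (SAP 9.3). A reader could therefore examine the exclusions to some extent. Appendix 2 is not in the text reviewed, and that is no fault of the plan.

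Finally, little rests on the PPASB. No formal hypothesis test is planned (Protocol 10.2), Phase A is the primary analysis, and safety and bone imaging use other sets.

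All of this stands and limits the weight of the point. None of it supplies the missing statement that the reviewers were masked, or an objective rule in its place.

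**Conclusion.** The point holds as a limited one. Exclusion from the PPASB on pain-medication grounds was a matter of judgement, exercised after the sponsor was unblinded, by reviewers whom nothing required to be masked. Knowledge of assignment could have influenced one of the two Pain NRS MMRM sets. That it did so is not shown.

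The FASB result, the rule-based PPASB exclusions and the safety analyses are not touched. The illustrative shift of about 0.02 to 0.29 SD rests on assumed arm sizes, exclusion counts and distances from the mean, with all exclusions in one arm and one direction. It ranges from negligible to a little over one standard error of the difference. It is not an estimate of bias in this trial.

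**What to change.** 1. In SAP 7.5 and 9.2, derive the pain-medication exclusions by program from recorded medications, using the lists in Protocol 7.6 and Appendix 1. Protocol 7.5 already collects name, indication, route, dose and frequency, so the permitted indications can be handled. The lists are not exhaustive, so the SAP must state which coded terms count. Alternatively, have staff without treatment access repeat the review on a listing without codes.
2. State in SAP 9.2 whether those who made the existing decisions were masked.
3. Tabulate PPASB exclusions by arm and reason. The set counts in SAP 9.1 are already planned; the reasons by arm are the addition.
4. State in SAP 12 that the FASB carries the Phase B Pain NRS conclusion and that the PPASB is supportive.

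Cost: a programmed rule or a masked re-review of the relevant deviations, one table and a few sentences. No new data are needed. The downside is that the PPASB list may change slightly.

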9.3 Demographics and Other Baseline Characteristics

Demographic and baseline characteristics of subjects in Phase B, including sex, race, ethnicity, age at baseline, weight, height, body mass index, KL grade, WPI, SSQ2, and mJSW, will be presented overall and by treatment group. Continuous variables will be summarized with descriptive statistics and categorical variables will be summarized with frequencies and percentages. The summaries will be provided for the FASB and PPASB. Subject-level listings will be provided.

9.4 Medical History

A summary of medical history by MedDRA system organ class was provided in the Phase A analysis. A subject-level listing will provide further information on each event.

10 GENERAL SAFETY ANALYSIS

Whereas Phase A analysis (defined prior to unblinding) was the primary analysis for this study, data collected during Phase B complements the primary analysis by offering insight into safety after more than one year of treatment.

10.1 Adverse Events

AEs collected in this study are events that occur during the course of the study that are not present prior to Day 1 study medication injection, or, if present at the time of study medication injection, have worsened in severity during the course of the study. AEs will be presented in summary tables depicting the number and percent of unique subjects experiencing each AE and the number of AEs overall and within each treatment group. The following summaries will be provided for both the entire study length (SAS) and for Phase B (SASB) separately:

- All AEs by seriousness, severity, and relationship to study product
- AEs by highest degree of seriousness, severity, and relationship to study drug
- AEs by MedDRA system organ class and preferred term
- AEs and SAEs by preferred term incidence
- Target-knee-related AEs and SAEs by preferred term incidence
- SAEs in subjects diagnosed with COVID-19

Subject-level listings will be provided for all AEs and all SAEs separately.

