5.5.2 HANDLING OF PARTICIPANT WITHDRAWALS OR TERMINATION

In case of premature discontinuation of study participation, ET procedures should be conducted within 14 days of discontinuation for any subject who discontinues after the Day 1 visit, if possible. The date the subject is withdrawn from the study and the reason for the discontinuation should be recorded on the eCRF. The Investigator or designee must complete all applicable eCRF pages for subjects who discontinue from the study prematurely.

Replacement of subjects who withdraw or discontinue prematurely is not allowed.

Subjects who are withdrawn from study medication for safety reasons will continue with all planned study visits per protocol, without any further dosing.

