6.1.9 DURATION OF THERAPY

The injectable investigational product or placebo is to be administered as a single intra-articular injection into the target knee joint once each at Day 1 and Week 24 (Phase A), and once each at Week 52 (EOSa) and Week 76 (Phase B).

At the Week 24, 52 (EOSa), and 76 visits, the Investigator should evaluate the subject for suitability to receive the study medication injection. The subject should not have any condition, including laboratory findings and findings in pre-injection assessments, that, in the opinion of the Investigator, constitutes a risk or contraindication for the injection, or that could interfere with the study objectives, conduct, or evaluation. The injections may occur up to two weeks later than the Week 24, 52 (EOSa), and 76 visits, respectively, to allow for resolution of any intercurrent illness (e.g., infection) prior to the injection. If, in the opinion of the Investigator, the subject should not receive any of the injections, the subject will discontinue treatment but will continue with all planned study visits per protocol.

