3.2.5 Phase B General Safety Endpoints

1. AEs, SAEs, vital signs, and clinical laboratory measures from Week 52 through Week 104

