7.6 Safety Analysis Set

The Safety Analysis Set (SAS) includes all subjects who received at least one study injection. Subjects will be analyzed as treated on Day 1 for the SAS. In this study, the FAS and SAS are identical, but for consistency with other studies, the SAS will be used in summaries of safety.

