7.7 Safety Analysis Set Phase B

The Safety Analysis Set Phase B (SASB) includes all subjects who received at least one study injection in Phase B. Subjects will be analyzed as treated on Day 1 for the SASB. In this study,

the FASB and SASB are identical, but for consistency with other studies, the SASB will be used in summaries of safety.

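### The Phase B adverse-event tables leave out anyone followed after Week 52 without a Phase B injection, and the whole-study tables give crude percentages over mixed one- and two-year follow-up

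*SAP*

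**What the plan says.** The Phase B general safety endpoint (SAP 3.2.5, Protocol 4.2.5) is "AEs, SAEs, vital signs, and clinical laboratory measures from Week 52 through Week 104". It sets no condition that the subject was injected in Phase B.

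SAP 10.1 defines the adverse-event tables: "The following summaries will be provided for both the entire study length (SAS) and for Phase B (SASB) separately". The two sets are:

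- SAP 7.6: "The Safety Analysis Set (SAS) includes all subjects who received at least one study injection".
- SAP 7.7: "The Safety Analysis Set Phase B (SASB) includes all subjects who received at least one study injection in Phase B".

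On follow-up without dosing, Protocol 5.5.2 says: "Subjects who are withdrawn from study medication for safety reasons will continue with all planned study visits per protocol, without any further dosing". Protocol 6.1.9 says that if the Investigator decides an injection should not be given, "the subject will discontinue treatment but will continue with all planned study visits per protocol". Protocol 4.1 opens Phase B to subjects who complete Phase A, and Protocol 7.3.4 makes the Week 52 injection depend on a suitability assessment.

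On the measure, SAP 10.1 says: "AEs will be presented in summary tables depicting the number and percent of unique subjects experiencing each AE", together with the number of events. SAP 14.2 summarises exposure as the number of injections received. Neither section provides time at risk, an exposure-adjusted rate or a time-to-event summary.

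**The concern.** There are two separate problems.

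**Who is counted.** Protocol 5.5.2 and 6.1.9 deliberately keep subjects in follow-up after injections stop. The Phase B tables then drop any such subject who had no Phase B injection. One reason for withholding an injection is a condition that makes it risky, so these subjects may differ in adverse-event risk from those who were injected. Their events after Week 52 appear in summary form only in the whole-study tables, combined with Phase A events.

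**What is divided by what.** Phase B needs separate consent. Non-entrants contribute about one year and entrants about two, yet the whole-study table counts each as one subject in the denominator. If one arm has more entrants, it has more time in which to record an event and shows a higher percentage at the same underlying rate.

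At stake is the reading of secondary objective 3 (safety, tolerability and effectiveness from 52 to 104 weeks) and of the whole-study adverse-event comparison.

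**Working it through.** The plan states no adverse-event rate, Phase B entry rate or count of uninjected Phase B subjects, so there is no figure of its own to reproduce here. The first part is a comparison of text. The second is arithmetic on stated assumptions.

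**Part 1: path of one subject**

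1. Completes Phase A and consents to Phase B (allowed by Protocol 4.1).
2. Is judged unsuitable for the Week 52 injection (Protocol 7.3.4 and 6.1.9).
3. Stops treatment but keeps all planned visits (Protocol 6.1.9). Adverse events are collected to the final visit (Protocol 8.3).
4. Has no Phase B injection, so is outside the SASB (SAP 7.7) and outside the Phase B tables (SAP 10.1).
5. Has had at least one study injection, so is in the SAS and in the whole-study tables.

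A subject injected at Week 52 and stopped before Week 76 fails step 4 and stays in the SASB.

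Illustration (all counts assumed): 40 subjects in an arm are followed in Phase B, 10 injected subjects have an event, and k uninjected subjects each have one. This is the extreme case for the uninjected group.

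| k | All followed, (10 + k)/40 | SASB, 10/(40 − k) |
|---|---|---|
| 1 | 27.5% | 25.6% |
| 2 | 30.0% | 26.3% |
| 4 | 35.0% | 27.8% |

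With k = 0 the two columns agree.

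**Part 2: crude percentage over mixed follow-up**

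Assumptions: 50 per arm (the planned size), the same constant event rate h per year in both arms, one year of follow-up without Phase B and two with it, and no dropout within a phase. With p the proportion entering Phase B:

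crude percentage = p(1 − e^(−2h)) + (1 − p)(1 − e^(−h))

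At h = 0.10, the one-year risk is 1 − e^(−0.1) = 9.5% and the two-year risk is 1 − e^(−0.2) = 18.1%.

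| Entry, arm 1 v arm 2 | Crude percentage | Ratio | Gap in subjects (of 50) |
|---|---|---|---|
| 70% v 70% | 15.5% v 15.5% | 1.00 | 0 |
| 75% v 65% | 16.0% v 15.1% | 1.06 | 0.4 |
| 80% v 60% | 16.4% v 14.7% | 1.12 | 0.9 |
| 90% v 70% | 17.3% v 15.5% | 1.11 | 0.9 |

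With equal entry the arms agree, but 15.5% is neither 9.5% nor 18.1%.

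The absolute gap grows for commoner events. For 90% versus 70% entry, a one-year risk of 30% gives 48.9% v 44.7% and a one-year risk of 50% gives 72.5% v 67.5%, gaps of 4.2 and 5.0 points. Subject-years are 50 × 1.9 = 95 versus 50 × 1.7 = 85, a ratio of 1.12. Expected events per subject-year are equal in the two arms.

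**How likely is such an entry gap by chance?** With 70% entry in both arms, the standard error of the difference is √(2 × 0.7 × 0.3/50) = 0.092.

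- Gap of 10 points or more: 28% (normal) to 33% (exact binomial).
- Gap of 20 points or more: 2.9% (normal) to 3.8% (exact binomial).

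**The case against.** The strongest reply is that little is lost and the stakes are secondary.

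- **Objective.** The primary objective is safety through 52 weeks. Its analysis had its own SAP and was complete, and SAP 10 describes Phase B as complementing it. A reader might infer that the primary safety conclusion is compromised. The documents do not support that, because these tables do not feed it.
- **Events are not lost.** Uninjected subjects' events are in the whole-study tables and in separate AE and SAE listings, and SAP 8.1 says the listings cover both phases. Vital signs and laboratory measures (SAP 10.2, 10.3) and bone imaging (SAP 11) are already on the SAS. The gap is confined to the Phase B adverse-event tables.
- **The group may be empty.** Protocol 4.1 says each consenting subject will receive the Week 52 injection, Protocol 6.1.9 allows up to two weeks' delay for intercurrent illness, and SAP 9.2 dates some Phase B deviations from that injection. The documents also do not settle whether someone stopped during Phase A has Phase B visits among the planned ones.
- **The format is common.** An injected-subject safety set for an extension is defensible. Counts and percentages are ordinary, and disposition by arm (SAP 9.1) lets a reader see unequal entry.

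Most of this stands and limits the size of the point. It does not close the gap. Listings give no Phase B percentage by arm, disposition does not convert to time at risk, and the SAS basis used for the other measures in the same endpoint makes the SASB-only choice for adverse events the exception.

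**Conclusion.** Both parts hold on the text, with a modest effect.

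The Phase B tables omit any subject followed after Week 52 without a Phase B injection. How many there are is unknown and may be none. It would be tempting to say the tables drop everyone taken off injections for safety. That is too broad: those injected at Week 52 and stopped later remain in, and Protocol 6.1.9 also allows an injection to be withheld for reasons other than safety.

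The whole-study percentage mixes one- and two-year risks even when entry is balanced. It would also be tempting to call the arm comparison confounded outright. The distortion arises only if Phase B entry or dropout differs by arm. Under constant and equal hazards of 0.10 per year, a 10-point entry gap gives a ratio of about 1.06, less than half a subject per arm of 50. A 20-point gap gives about 1.11 to 1.12 but would occur by chance in only about 3 to 4% of trials at 70% entry. A gap caused by treatment could be larger or smaller, and the documents give no information on it.

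The change is worth making for secondary objective 3 and the whole-study table. It has no bearing on the completed Phase A primary safety analysis.

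**What to change.** In SAP 10.1:

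1. Produce the Phase B AE and SAE tables for all SAS subjects with any follow-up after Week 52, and keep the SASB table as a subset. State the start of the Phase B window in a way that also works for a subject with no Week 52 injection, for example the Week 52 visit date. Report by arm how many subjects are in the wider set but not in the SASB. If that number is zero, a footnote is enough.
2. Add subject-years of follow-up and events per 100 subject-years by arm to the whole-study and Phase B tables, beside the existing counts and percentages.

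The cost is revised SAP wording, one further set of Phase B tables and a few extra columns, all from dates already collected. No new data are needed and study conduct does not change.
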